After baseline phenotyping, subjects will be placed on a low fat (20±5% protein, 25% fat, 55±5% carbohydrate), weight maintenance diet from the metabolic research kitchen. Total caloric requirements will be estimated by the research dietitian. Due to the low proportion of body fat in people with lipodystrophy, all male and female subjects' energy needs will be estimated using the Mifflin St. Joer equation for males with an activity factor of 1.3. Upon admission, resting energy expenditure will be measured and dietary energy will be adjusted as needed. The diet may be adjusted during the first few days, but will be continued for the remainder of the study without change.

In the leptin naïve group, appetite is expected to decrease following leptin initiation during Period 2, although the early time course of this effect is not known. Subjects will be encouraged to eat all food presented to them by the metabolic kitchen in order to maintain the isocaloric nature of the diet throughout both periods. However, if they are unable to consume all food, the uneaten portion will be returned to the metabolic kitchen and weighed to document the extent of deviation from the isocaloric diet. Analogously, in the leptin-treated group, subjects may feel hungry after leptin withdrawal, but will only be permitted to eat the food provided by the metabolic kitchen.

In prior studies of leptin replacement in lipodystrophy, subjects had a mean weight loss of only 2.8 kg (4.6% of initial body weight) after 4 months of leptin replacement. Hence, changes in body weight during the course of the 3 week inpatient portion of this study are not expected to be clinically significant. Because each subject will be compared with him/herself in the leptin deficient versus leptin replaced state, maintaining constant (isocaloric) food intake during both conditions will allow assessment of the energy-intake independent effects of leptin.

Medications

Leptin Treatment

Any subject starting leptin on this study will get it through NIH under IND, regardless of whether or not they fit in an FDA approved category. After the follow-up visits, subjects who are eligible will be transitioned to commercial drug supply through their physician. Subjects undergoing leptin withdrawal may receive leptin under IND or FDA approved commercial drug, depending on the timing of their study participation.

Details of leptin administration and dosing for the subjects who are leptin treated are as follows:

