The dose of metreleptin will be increased beyond 5 mg twice daily (or 0.15 mg/kg/day in patient under 50 kg) only if there is a clear decline in metabolic status without alternative explanations for the metabolic change (such as an infection, noncompliance or dietary indiscretion). It is important to note this because of the wide range of variation in the clinical presentation of these patients, it is impossible to define pre-determined thresholds of metabolic parameters that would appropriately guide dose modifications. Instead, the PI will use best clinical judgment to make dose modifications based on the constellation of metabolic and clinical data available for each patient. Dose escalations will be capped such that the total dose administered will not exceed 0.24 mg/kg/day for any patient without seeking prior permission from the FDA, the NIDDK/ NIAMS IRB and Aegerion Pharmaceuticals, the manufacturer of Metreleptin. If subjects do not tolerate a higher dose level, they can continue the study at the next lowest tolerated dose. Based on previous clinical experience with Metreleptin, tolerance to Metreleptin at doses between 0.12-0.24 mg/kg/day is not expected to be an issue.

Dose reduction:

The dose of metreleptin will be decreased if a subject experiences excessive weight loss (BMI below the normal range for age and sex, or a lesser degree of weight loss that is distressing to the patient). Doses will also be decreased if a subject experiences injection site reactions that cannot be controlled with antihistamines and/or analgesics.

Leptin Withdrawal

For leptin treated subjects, the last dose of leptin will be given on the final day of Period 1 (Day -1) at either 8 am or 8 pm, depending on whether the subject receives once or twice daily dosing. No leptin will be given during Period 2 (Days 0-13). Leptin will be resumed on the morning of Day 14 at the previous dose. In patients who were treated with leptin under protocol 02-DK-0022, we typically recommend tapering of leptin over a 1 week period in patients who stop leptin treatment in an outpatient setting. In contrast, in this protocol, leptin will be stopped without a taper under inpatient observation. The risks of stopping leptin are discussed under Risks.

Pre-study Medications

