Non-serious protocol deviations will only be reported to the NIDDK/ NIAMS IRB (within 14 days after the PI first learns of the event) if they represent a departure from NIH policies for the conduct of human subjects research, adversely affect the health care of the subject(s) or compromise the interpretation or integrity of the research. Non-serious protocol deviations that result from normal subject scheduling variations or technical issues associated with sampling that does not impact the health of the subject or the interpretation of the study data will not be reported.

Adverse Events

An ***Adverse Event (AE)*** is defined as any new untoward medical occurrence or worsening of a preexisting medical condition in a clinical investigation subject administered an investigational (medicinal) product and that does not necessarily have a causal relationship with this treatment. An AE can therefore be any unfavorable and unintended sign (such as an abnormal laboratory finding), symptom, or disease temporally associated with the use of investigational product, whether or not considered related to the investigational product.

The causal relationship to study drug is determined by a physician and should be used to assess all adverse events (AE). The causal relationship can be one of the following:

Related: There is a reasonable causal relationship between study drug administration and the AE.

Not related: There is not a reasonable causal relationship between study drug administration and the AE.

The term "reasonable causal relationship" means there is evidence to suggest a causal relationship. Adverse events can be spontaneously reported or elicited during open-ended questioning, examination, or evaluation of a subject. (In order to prevent reporting bias, subjects should not be questioned regarding the specific occurrence of one or more AEs.)

Non-Serious Adverse Event Collection and Reporting

The collection of non-serious AE information should begin once a subject's written consent to participate in the study has been obtained. Any significant worsening noted during interim or final physical examinations,

electrocardiogram, x-ray filming, any other potential safety assessment required or not required by protocol should also be recorded as a non-serious or serious AE, as appropriate, and reported accordingly.

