
Should a patient become pregnant while on study, per 45 CFR 46.204, (1) no inducements, monetary or otherwise, will be offered to terminate a pregnancy, (2) individuals engaged in research will not be involved in any decisions as to timing, method, or procedures used to terminate a pregnancy, and (3) individuals engaged in the research will have no part in determining viability of a neonate.

The investigator must immediately notify the Aegerion Pharmaceuticals (or designee) Medical Monitor of this event and complete and forward a Pregnancy Surveillance Form to United Biosource Corporation (UBC) (or designee) within 7 business days via email to [contact] and [contact].

Follow-up information regarding the course of the pregnancy, including perinatal and neonatal outcome and, where applicable, offspring information must be reported on the Pregnancy Surveillance Form. Any pregnancy that occurs in a female partner of a male study participant should be reported to the sponsor. Information on this pregnancy will be collected on the Pregnancy Surveillance Form.

Overdose

An overdose is defined as the accidental or intentional administration of any dose of a product that is considered both excessive and medically important. All occurrences of overdose must be reported as an SAE.

Serious Adverse Event Collection and Reporting

Following the subject's written consent to participate in the study, all SAEs, whether related or not related to study drug, must be collected, including those thought to be associated with protocol-specified procedures. All SAEs must be collected that occur within 30 days of discontinuation of dosing. The investigator should report

any SAE that occurs after these time periods and that is believed to be related to study drug or protocol-specified procedure.

An SAE report should be completed for any event where doubt exists regarding its seriousness. If the investigator believes that an SAE is not related to study drug, but is potentially related to the conditions of the study (such as withdrawal of previous therapy or a complication of a study procedure), the relationship should be specified in the narrative section of the SAE Report Form.

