For leptin-treated patients who are withdrawing from leptin, this study is of greater than minimal risk, and without prospect of direct benefit to subjects, but likely to yield generalizable knowledge about the subjects' condition, e.g. lipodystrophy. For those in the leptin naïve arm of the study, there is a prospect of direct benefit. Based on these criteria, mature adolescents ages 14-17 years will be permitted to participate in the leptin-naïve arm of the study. Even though there is the potential for clinical benefit, younger children and adults who are unable to give informed consent are unlikely to possess the emotional maturity to participate in such a complex and time-consuming study. Because the risk of pancreatitis with leptin withdrawal represents greater than a minor increment over minimal risk, children will not be enrolled in the leptin withdrawal arm of the study. As we gain more experience in risks of leptin withdrawal in adults, we may request NIDDK/NIAMS IRB permission to include children in this arm in the future. Adults over age 70 years are excluded in order to decrease inhomogeneity related to an aging population. Because there is no prospect for direct benefit, adults who are unable to give informed consent will not be eligible.

Withdrawal Criteria

1. **Withdrawal of consent.** A subject wishes to withdraw from the study as stated in the informed consent (all subjects reserve the right to withdraw from the study without prejudice).
2. **Adverse event.** A subject experiences an adverse event that in the investigator's opinion necessitates withdrawal from the study. Specific examples of adverse events that would result in withdrawal are:
 - a) Pancreatitis during the leptin withdrawal period in the leptin treated group. Pancreatitis is a clinical diagnosis, and will be suspected in the presence of moderate to severe abdominal pain accompanied by nausea and/or vomiting. If pancreatitis is suspected, amylase and lipase levels will be drawn, and GI consultation obtained. However, even if amylase and lipase levels are normal, in the presence of typical signs and symptoms of pancreatitis, leptin will be restarted.
 - b) Diabetic ketoacidosis during the leptin withdrawal period in the leptin treated group
3. **Investigator decision.** An investigator feels it is in the subject's best interest to terminate participation. The detailed reasoning behind this decision will be documented.

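### Adverse-event causality is coded only against giving study drug, so the code cannot attribute an event to leptin withdrawal, which is the intervention in the leptin treated group

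*Combined protocol and SAP*

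**What the plan says.** The Adverse Events section sets the rule and its scope: "The causal relationship to study drug is determined by a physician and should be used to assess all adverse events (AE"). It offers two categories and no third. An event counts as related under this wording: "Related: There is a reasonable causal relationship between study drug administration and the AE". The remaining category simply reverses that test and keeps the same reference to giving the drug: "Not related: There is not a reasonable causal relationship between study drug administration and the AE".

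The Leptin Withdrawal section describes the leptin treated group after the end of Period 1: "No leptin will be given during Period 2 (Days 0-13"). Leptin is resumed on the morning of Day 14.

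The protocol expects harm from stopping. Rationale for Subject Selection bars minors from this arm with the words "Because the risk of pancreatitis with leptin withdrawal represents greater than a minor increment over minimal risk". Glucose Management anticipates hyperglycemia during withdrawal.

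Serious Adverse Event Collection and Reporting contains the one provision that links an event to stopping treatment. It covers an SAE that the investigator believes is unrelated to study drug but possibly related to study conditions, and it gives withdrawal of earlier therapy as an example. For such an event, "the relationship should be specified in the narrative section of the SAE Report Form". The sections on non-serious events and on laboratory abnormalities contain no similar provision.

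**The concern.** A causality code is useful only if it refers to the exposure under study. In the leptin naïve group that exposure is leptin being given, and the scale fits. In the leptin treated group during Period 2 the exposure is leptin being withheld, and the scale has no category for it. Both categories ask about drug administration, so a physician who follows the text must code a withdrawal harm as not related.

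What is at stake is how the safety data of this arm can be read. The protocol describes the arm as carrying more than minimal risk with no prospect of direct benefit, so attribution to the intervention is a natural safety question there. A listing or table by relatedness would put true withdrawal harms in the same cell as incidental events, and the error would run in one direction.

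**Working it through.** No figure in the plan depends on this point, so there is no calculation to reproduce. The check is a comparison of sections.

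1. **Scope.** The causality rule covers all adverse events, serious or not, in both groups.
2. **Structure.** The two categories are complements: an event either has a reasonable causal relationship to drug administration or it does not. Every event therefore receives one of the two codes.
3. **Exposure in the leptin treated group.** Days 0 to 13 inclusive are 13 − 0 + 1 = 14 days without leptin. An event caused by the absence of drug is not caused by its administration. It fails the first category and meets the second.
4. **Could administration be read to include stopping?** The protocol's own usage says no. The SAE section places an event due to withdrawal of earlier therapy among those believed not related to study drug, and then asks for a narrative note.
5. **Routes for attributing an event to withdrawal:**

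| Event in the leptin treated group, Period 2 | Coded category, read literally | Other route in the visible text |
|---|---|---|
| SAE caused by withdrawal | Not related | Free text in the SAE narrative |
| Non-serious AE caused by withdrawal | Not related | None specified |

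6. **What depends on the code.** All adverse events are recorded and summarized at annual review. All non-serious events go on the case report form, as do clinically significant laboratory results and those needing corrective therapy. All SAEs are collected and sent to the manufacturer whether or not related, and collection runs to 30 days after dosing stops. That window covers the 14-day withdrawal period. Likely or confirmed pancreatitis during withdrawal leads to IRB notification. Only SAEs arising after the collection window are reported according to relatedness, and that test also covers protocol-specified procedures.
7. **Reach.** The plan enrolls up to 20 subjects per group to obtain 10 completers. The affected exposure is therefore at most 20 × 14 = 280 subject-days, and 10 × 14 = 140 among 10 completers.

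Steps 1 to 5 establish the misclassification. Step 6 confines it to the code and to anything tabulated from it.

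**The case against.** The strongest reply is that little hangs on the code. Recording, annual summary and SAE reporting within the window proceed regardless of relatedness. The main serious harm is handled by name: pancreatitis and ketoacidosis during withdrawal are withdrawal criteria, and lipase and amylase are checked about every other day. Glucose and triglycerides are study outcomes, drawn every other day and compared within subject on and off leptin, so the effect of withdrawal on them is estimated directly. No visible section plans a table by relatedness, and a reader who knows the arm and period can identify events that occurred off drug.

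Most of this stands, and it rules out the inference that withdrawal harms would go unrecorded or unreported. It does not repair the rule. Sorting by arm and period shows when an event happened but not why: Period 2 also contains a clamp, tracer infusions and repeated blood sampling, and their complications would be mixed with withdrawal harms. A code that every event must carry should not give the wrong answer for one arm.

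Two further inferences are tempting and should not be drawn.

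- A reader might infer that the adverse-event definition itself excludes this arm, because it refers to a subject given an investigational product while "Subjects undergoing leptin withdrawal may receive leptin under IND or FDA approved commercial drug". These subjects receive leptin through Day -1 and again from Day 14, non-serious event collection starts at written consent, and nothing in the visible text excludes events in subjects on commercial supply.
- A reader might infer that miscoding would drive a decision about minors, since the protocol says "As we gain more experience in risks of leptin withdrawal in adults, we may request NIDDK/NIAMS IRB permission to include children". That sentence refers to experience in general. It does not say that a request would rest on a count of related events, and the IRB receives adverse event information each year.

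**Conclusion.** The point holds as a classification fault. The causality scale applies to all adverse events but cannot attribute one to leptin withdrawal. Followed literally, it codes withdrawal harms in the leptin treated group as not related throughout the 14 days of Period 2. For SAEs the true link survives only as free text. For non-serious events the visible text gives it no place.

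The size cannot be put as a number of events. The documents give no rate of withdrawal-related adverse events. The only experience cited, at least 25 earlier discontinuations, reports no serious event from acute withdrawal and does not give a count of non-serious ones. What can be said is that every withdrawal-caused event coded by the letter of the rule is misplaced, whatever the rate.

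The conclusion assumes that physicians apply the categories as written. If some do not, coding becomes inconsistent, and the relatedness count for this arm is still unreliable. It also rests on the visible text. The NIH procedure cited for event definitions and the case report forms are not in the documents, and parts of the risk section are absent from the public copy. An attribution field may already exist on the forms. If so, the protocol wording should be brought into line with it.

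**What to change.** Either of two changes is enough.

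- In the Adverse Events section, define both causality categories against the study intervention: leptin given, or leptin withdrawn in the leptin treated group.
- Keep the present scale and add a coded item, related to leptin withdrawal (yes or no), for both non-serious events and SAEs, aligned with the existing SAE narrative provision.

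The second keeps drug relatedness and withdrawal relatedness apart. That is useful because the leptin treated group also receives leptin in Period 1 and from Day 14, and because the SAE section refers to relationship to study drug elsewhere. With either change, show withdrawal-related events separately in the annual summary to the IRB. The adverse-event definition needs no change.

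The cost is a wording change or one extra form item. The related-event count in the withdrawal arm may rise, which would reflect corrected attribution and not new harm. Dosing, schedule, sample size and clinical management are unaffected.

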Because of the risk of pancreatitis with leptin withdrawal, our group has recommended that patients discontinuing leptin in the outpatient setting (in the absence of physician supervision) gradually taper the dose over one week. In this study, in order to more rapidly test the effects of leptin withdrawal, we plan to discontinue leptin without tapering. Leptin has been discontinued in at least 25 other lipodystrophy patients, either based on patient decision (e.g. non-compliance or personal choice) or joint patient-investigator decision. In half of these patients, leptin was tapered over 1 week, and in the other half it was stopped without a taper. None of these patients had any serious adverse event resulting from acute leptin withdrawal, although long-term (months to years) worsening of metabolic parameters (A1c, triglycerides, ALT/AST) and other adverse events related to the natural history of lipodystrophy were observed. Based on these observations, we estimate that the risk of pancreatitis during short-term leptin withdrawal is low, but non-zero. The following measures are being taken to minimize the risk of pancreatitis to patients undergoing leptin withdrawal in this study:

- i. Subjects at increased risk of pancreatitis are excluded, as follows:
 - a. **Triglycerides over 2000 mg/dL at initiation of leptin treatment.** This will exclude patients with extreme hypertriglyceridemia at baseline, who would be more likely to rebound to high levels with leptin withdrawal, regardless of their current triglyceride control or history of pancreatitis.

- d. **Current lipase > 491 units/L (the upper limit of normal in the NIH assay).** While both amylase and lipase are often used clinically in the assessment of pancreatitis, amylase is a non-specific test that may be elevated for other reasons. Subjects with elevated lipase at study entry will be considered to have laboratory findings consistent with pancreatitis, and will be excluded.

ii. The key element that will minimize risk to subjects is that leptin withdrawal will be performed under close inpatient observation with a controlled diet that should help maintain lower blood glucose and triglycerides. Clinical and laboratory monitoring of subjects for pancreatitis will be performed throughout the period of leptin withdrawal, as follows

- a. Safety labs will be monitored approximately every other day (when research labs are obtained. These will include amylase, lipase, and stool pancreatic elastase. Elevated lipase (greater than the upper limit of normal, 491 units/L) will be a withdrawal criterion. Elevated amylase will be used only as a supportive criterion. Stool pancreatic elastase will be measured primarily for research purposes, as a marker of pancreatic exocrine function. Although triglycerides will be measured along with these labs, isolated elevation of triglycerides, without signs or symptoms of pancreatitis or elevated lipase, will not be a withdrawal criterion.
- b. If pancreatitis is clinically suspected (either based on signs/symptoms consisting of moderate to severe abdominal pain with nausea or vomiting, or based on lipase), the following will take place:
 - i. Amylase and lipase levels will be drawn
 - ii. GI consultation will be obtained
- c. If a diagnosis of pancreatitis is likely or confirmed based on labs and/or GI consultation, the following additional actions will be taken
 - i. Appropriate treatment will be initiated based on GI recommendations (usually, NPO and pain medications)
 - ii. Leptin will be restarted immediately
 - iii. The patient will be withdrawn from the study
 - iv. The IRB will be notified per guidelines for SAEs

4. **Blood Sampling:** Peripheral blood draws (venipuncture) performed during this study for research will not exceed 10.5 mL/kg, or 550 mL (whichever is smaller) per 8-week period for adults. For pediatric

patients, blood draws will not exceed 5 mL/kg in a single day, or 9.5 mL/kg or 550 mL (whichever is smaller) per 8 week period. Patients may experience some discomfort at the site of the needle entry, and there is a risk of bruising at the site. There is a remote risk of fainting or local infection.

5. Oral Glucose Tolerance Test: Patients will be required to drink a very sweet glucose containing beverage. This may be associated with mild nausea or distaste. Due to serial blood draws, an intravenous line will be placed, with attendant risks of discomfort and possible skin infection.
6. Euglycemic Hyperinsulinemic Clamp Study: In order to assess insulin sensitivity, patients will receive an intravenous infusion of insulin and – via a second intravenous access – increasing amounts of glucose to maintain euglycemia. Insertion of the necessary intravenous lines may cause the above-mentioned discomfort and a possible skin infection. Insulin infusion can induce hypoglycemia and hypokalemia. Either event is very unlikely, since patients undergo frequent blood glucose measurements and are constantly observed for the presence of hypoglycemic symptoms by an experienced nurse and/or physician. However, in order to prevent complications, two patent, well-functioning intravenous lines are required during this procedure.
7. Glucose and Lipid Turnover: The stable isotopes C is not associated with any toxicity at the doses used in these studies ⁵³. Deuterium at the doses given may cause temporary dizziness. This risk will be minimized by dividing the ²H₂O dose into four aliquots, and by giving the doses at night while subjects lie in bed. If subjects need to get out of bed (e.g. to use the bathroom) the patient will first sit upright in bed for a few minutes prior to standing, and a nurse will be available to supervise and assist. Palmitate must be complexed to albumin prior to delivery, and thus carries the risks associated with use of human blood products. To minimize exposure to human albumin, uniformly labeled ¹³C₁₆ palmitate will be used, permitting use of the minimum possible dose of this tracer.
8. Resting Energy Expenditure: There are no significant risks associated with measurement of resting energy expenditure. Some patients may feel uncomfortable from lying still with a plastic hood over the head for approximately 30 minutes.
9. Actigraphy, heart rate variability, blood pressure monitoring, and skin temperature: There are no significant risks associated with actigraphy, or monitoring of heart rate, blood pressure, or skin temperature. Some patients may find it an inconvenience to wear the devices.
10. DEXA Scan: The effective radiation dose with total body DEXA scanning is 0.00001 rem. This is equivalent to average daily background radiation from natural sources, and is not thought to increase lifetime cancer risk. Subjects in this study will have up to three DEXA scans (total radiation dose 0.00003 rem) per year.
11. Magnetic Resonance Imaging (MRI) and Magnetic Resonance Spectroscopy (MRS): While MR scanning is thought to be safe, the procedure may cause anxiety in some patients since current equipment used at the Clinical Center uses a closed tube. Adult patients will be offered sedatives such as Valium if they express worry about being in a closed space. Conscious sedation will not be employed on adolescents to perform any of these tests. Parental support will be sought if adolescents find it hard to stay immobile for the duration of the studies. No intravenous contrast will be used in these studies.
12. 24 hour urine collection: Urine collection may be slightly inconvenient for subjects; however, there is no health risk.

13. Metabolic Chamber: Some inconvenience can reasonably be expected as a result of spending an extensive time (24 hours) in the live-in room calorimeter. However, the risk to subjects' health is minimal.
14. Ultrasounds: The pelvic ultrasound may be uncomfortable due to pressure on a full bladder but there are no risks.
15. Echocardiogram: The echocardiogram may be inconvenient but there are no risks to the subject's health.

Alternatives to participation

Participation in clinical trials is completely voluntary. Refusal to participate will not affect a subject's ability to participate in other studies of leptin and lipodystrophy at NIH or elsewhere.

Financial Compensation

All subjects will receive financial compensation for their time per Clinical Center guidelines for on-site visits, and additional compensation will be provided for specific procedures based on inconvenience units, as follows:

Procedure	Inconvenience Units	Compensation	Short-term (3 week) study		Long-term follow-up visit	
			Occurrence	Total	Occurrence	Total
Inpatient per diem	n/a	\$40	20	\$800	4	\$160
Metabolic Chamber	5	\$50	3	\$150	1	\$50
DEXA	1	\$10	2	\$20	1	\$10
Exercise test	1	\$10	3	\$30	1	\$10
Euglycemic Clamp	5	\$50	2	\$100	1	\$50
Tracer studies	2	\$20	3	\$60	1	\$20
LH pulsatility	3	\$30	2	\$60	1	\$30
MRI/MRS	3	\$30	2	\$60	1	\$30
Total				\$1280		\$410

Consent/Accent Procedures

Written consent/assent will be obtained from each subject after detailed explanations of the planned procedures by the principal or an associated investigator in language understandable to the subject. The consent process will take place prior to any study procedures. Sufficient time and opportunity will be given for discussion of the research as well as to answer any questions the subject may have, taking care to minimize or eliminate the perception of coercion or undue influence. The participant and the investigator will sign the current IRB-approved informed consent document. A copy of the consent will be given to the subject for future reference and the consenting process will be documented in the electronic medical record (CRIS).

Given the prospect of direct benefit for minor subject participants, only one parent/guardian or LAR will need to give written informed consent prior to any screening visits, study procedures or treatments. The Principal Investigator or other designated qualified protocol investigators will explain the study in

language understandable to the parent/guardian or LAR. If appropriate, the investigator will also explain the study to the minor who is of a younger age and level of understanding. Sufficient time and opportunity will be given for discussion of the research as well as to answer any questions they may have, taking care to minimize or eliminate the perception of coercion or undue influence. A witness will also sign the consent document to attest only to the validity of the signature of the parent/guardian or LAR, not the validity or quality of the consent. If appropriate, the investigator will have the minor will provide assent, and if possible, will sign the current IRB approved assent document. The investigator will sign the assent as well. A copy of the consent and assent will be given to the minor and his/her parent/guardian or LAR for future reference. The signed documents will be sent to the Medical Records Department for placement in the subject's permanent CC medical record. The consent process will additionally be documented in the electronic medical record (CRIS)

For patients currently enrolled on the protocol, that are turning of legal age (i.e. 18 years of age) and who are able to provide consent, we plan to follow the procedures outlined in NIH SOP 14D and the same procedures described above in order for the patient to continue receiving study drug without interruption.

We do not plan or anticipate the enrollment of non-English speaking subjects. However, they are not excluded from participation either. If there is unexpected enrollment of a research participant for which there is no translated extant IRB-approved consent document, the Principal Investigator and/or those authorized to obtain informed consent will use the short form consent process as described in MAS Policy M77-2, NIH SOP 12, 45 CFR 46.117 (b), and 21 CFR 50.27 (b). The summary that will be used is the English version of the extant IRB-approved consent document. We request prospective IRB approval of the use of the short form consent process for up to a maximum of 5 requests (either for individual participants or families of participants) in a given language, and will notify the IRB at the time of continuing review of the frequency of the use of the short form. Should we reach the threshold of 5 subjects and/or families speaking a single language, we will request an additional use of the short form from the IRB and will notify the Board that we plan to have any consent documents frequently used with that population translated into the language(s) they speak.

Subjects have the right to withdraw participation from this protocol at any time.

Research Use, Storage and Disposition of Human Subjects' Samples and Data

For future reference and potential use, we will store all samples (blood or fluids) in our locked freezers for an unlimited period of time. Samples will be labeled with coded identifiers linked to patient identity only via a secured database. Research records and data with personal identifiers will be stored in our locked offices, the medical record department, and the electronic study database. This material will additionally be protected by medical record and computer access procedures. Access to records and data associated with personal information will be restricted to the Principal Investigator, Co-Investigators, study support staff, and database support staff.

Stored samples and/or data may be sent to outside collaborating laboratories, or shared with other NIH collaborating investigators, to study questions related to lipodystrophy or its complications (including, for example: glucose metabolism, diabetes, obesity, weight, appetite, steatohepatitis, and lipid metabolism). Samples may be sent to outside commercial laboratories for analysis. Samples and data sent to outside laboratories and collaborators for analysis and/or testing will contain only coded numbers, without personal identifiers. Tech Transfer agreements will be completed before the exchange of samples and/or data with outside collaborators.

Subjects may request that unused samples be removed from our freezers and returned to the subject, or be destroyed. If no such request is made, we will keep samples until they are completely used or no longer of scientific value, at which time they will be destroyed. We do not plan to destroy personal medical information or stored data. The Principal Investigator will report loss or destruction of data or samples to the NIDDK/NIAMS IRB.

Material Transfer Agreement/Collaboration(s):

Collaboration has been established with [name], a board-certified pediatric endocrinologist and Professor of Pediatrics and Medicine at Baylor College of Medicine. Our direct site contact will be [name]. The purpose of the collaboration is to assist in the conduct of the clinical studies determining the rates of glucose production and gluconeogenesis in subjects with a variety of forms and severity of lipodystrophy. This will include the review of the protocol design, potentially the analysis of coded human subject samples, review of the coded data derived and interpretation of the results.

Collaboration has been established with [name] at the Mayo Clinic in Rochester, Minnesota. The purpose of the collaboration is to assess whether steroid synthesis and metabolism is altered in patients with lipodystrophy and effected by metreleptin treatment. This collaboration will involve transfer of coded human plasma and urine samples (not data), review of the coded data derived, and interpretation of the results.

